**Table 1 Recommended Infusion Rates**

Day 1 infusion	Total dose (mg)	Time (minutes)***	Day 15 infusion	Total dose (mg)	Time (minutes)***
50 mg/h	25	0-30	100 mg/h	50	0-30
100 mg/h	50	31-60	200 mg/h	100	31-60
150 mg/h	75	61-90	300 mg/h	150	61-90
200 mg/h	100	91-120	400 mg/h	700	91-196**
250 mg/h	125	121-150	-	-	-
300 mg/h	150	151-180	-	-	-
350 mg/h	175	181-210	-	-	-
400 mg/h	200	211-240	-	-	-
400 mg/h	100	241-255*			

\* Approximately at 255 minutes (4 hours 15 minutes) to complete the 1,000 mg total dose.

\*\* Approximately at 196 minutes (3 hours 16 minutes) to complete the 1,000 mg total dose.

\*\*\*Allowed window for infusion rate time: For each time point:  $\pm 5$  minutes (e.g. when start 50 mg/h for first course: 25~35 minutes can be allowed).

In the event that a patient experiences an infusion-related reaction or an adverse drug reaction (ADR), the infusion rate should be reduced to half the rate (e.g., from 100 mg/hour to 50 mg/hour). Once the infusion-related reaction or ADR has resolved, the Investigator should wait an additional 30 minutes while delivering the infusion at the reduced rate. If tolerated, the rate may be increased to the next closest rate on the patient's infusion schedule. Please refer to the following examples:

**(Example 1)** An infusion-related reaction or an ADR at a rate of 50 mg/h  $\rightarrow$  change rate to 25 mg/h  $\rightarrow$  reaction resolved  $\rightarrow$  additional 30 minutes at a rate of 25 mg/h  $\rightarrow$  change back to 50 mg/h.

**(Example 2)** An infusion-related reaction or an ADR at a rate of 300 mg/h → change rate to 150 mg/h → reaction resolved → additional 30 minutes at a rate of 150 mg/h → change back to 200 mg/h.

Drug infusions will take place under the close supervision of an experienced physician, and in an environment where full resuscitation facilities are immediately available. Although the study drug may be administered on an outpatient basis, patients may be hospitalized for observation at the discretion of the Investigator, and such instances of planned hospitalization will NOT be recorded as a serious adverse event (SAE).

Any drugs that are used to manage hypersensitivity reactions or ADRs, including but not limited to epinephrine, antihistamine, and corticosteroid, should be immediately available in case of emergency.

Attention should be given to the development of anaphylaxis during infusion of the study drug. When an anaphylactic reaction is suspected during infusion of the study drug:

- Discontinue the study drug.
- Apply a tourniquet close to the infusion site in order to slow systemic absorption of the study drug. Do not block artery flow.
- Perform appropriate airway management.
- If required, administer antihistamine, epinephrine, or other drugs.
- Closely monitor the patient and document the observations.

Patients who experience a moderate to severe infusion-related reaction (fever, chills or hypotension), should have their infusion interrupted immediately and should receive aggressive symptomatic treatment, such as glucocorticoids, epinephrine, bronchodilators or oxygen, as per local practice. Depending on the severity of the infusion reaction and the required interventions, patients should either have their infusion temporarily interrupted or be discontinued from the study treatment. The infusion should not be restarted before all the symptoms have disappeared, and then it should be restarted at half the rate. If the patient tolerates the reduced rate for 30 minutes then the infusion rate may be increased to the next closest rate on the patient's infusion schedule. If the subject does not tolerate the reduced rate for at least 30 minutes or, if the same severe (NCI-CTCAE Grade 3) infusion reaction occurs for a second time, the patient can be discontinued from the study treatment.

At the end of each infusion, the i.v. line is recommended to remain in place for at least 1 hour to allow infusion of i.v. drugs if necessary. If no AE occurs during this time, the i.v. line may be removed.

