**Figure 1 Study Design**

Standard arthritis assessments and safety assessments will be performed. A disease activity score based on a 28 joint count (DAS28) will be calculated by the study personnel at regularly scheduled visits. At least one experienced, independent joint assessor, blinded to other study assessments as well as the dosing regimen, will be identified at each study center to perform the swollen and tender joint counts.

A provision is made for patients to initiate “rescue therapy” with the use of one non-biologic DMARD after Week 16 of the study (see Section 3.2.6).

Patients with rheumatoid arthritis (<50% improvement from Baseline in both the swollen and tender joint counts) who have been followed up during Part A will be provided with

additional treatment of study drug with two 1,000 mg i.v. infusions (at Week 24 and Week 26 [14 days later]). Patients will attend the study center approximately every 12 weeks during Part B. Patient who are not eligible for the second course of study treatment will also attend all visits until week 52.

Patients may return for unscheduled visits if their medical condition requires immediate attention.

To prevent missing data in important supportive efficacy and safety analysis, patients who discontinued study treatment, will also attend all visits until week 52.

The primary safety concerns associated with rituximab are progressive multifocal leukoencephalopathy (PML), anaphylactic reactions, hepatitis reactivation, and severe mucocutaneous reactions. Patients will be monitored carefully for these during the study.

Any patient who is suspected of developing PML, anaphylactic reactions, hepatitis reactivation, and severe mucocutaneous reactions will be discontinued from the study treatment and the AE will be followed closely, at the discretion of the Investigator.

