#### **Second Infusion (Day 15 of First Course)**

Patients who experienced infusion-related reactions to the first infusion should receive study drug as per the initial infusion schedule, with the rate of infusion not exceeding half that associated with the prior reactions. If this reduced rate is tolerated for 30 minutes, then the infusion rate may be increased to the next closest rate following the infusion schedule.

Patients who miss the allocated day (Day 15  $\pm$  1 day) for the second infusion (the first infusion will be administered following randomization on Day 1) will be contacted and another visit arranged as soon as practically possible in order to administer study drug. Such cases will be considered protocol deviations (see Section 3.13).

If a patient experiences a new infection or other AE between the Day 1 and Day 15 infusions of any treatment, the Day 15 infusion should be delayed until the infection or AE has completely resolved and the Investigator considers it safe to resume treatment. A maximum delay of 15 days from the scheduled date of the second infusion is permitted. Patients who have a delay of >15 days in receiving the second infusion due to an AE or otherwise will be discontinued from the study treatment.

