### **3.2.3 Study Drug Administration (Part B)**

Patients with active rheumatoid arthritis (<50% improvement from Baseline in both the swollen and tender joint counts) who have been followed up during Part A will be provided with continued (or additional) treatment of rituximab.

Before subsequent dose, absolute neutrophil count must be  $\geq 1.5 \times 10^9/L$  and platelet counts must be  $\geq 75 \times 10^9/L$ . If the Absolute Neutrophil Count (ANC) value and platelet count are marginally lower, re-testing at an unscheduled visit may be performed at the discretion of the Investigator within the 4-week period between Week 20 and Week 24. In case Visit 11 is missed, all safety evaluations including ANC value and platelet count must be completed as an unscheduled visit for patient to be eligible for second course of infusion.

Eligible patients in the SAIT101 arm will receive additional SAIT101 treatment at Week 24 and Week 26. Eligible patients in the MabThera® arm will receive additional MabThera® treatment at Week 24 and Week 26. Eligible patients in the Rituxan® arm will be randomized in a 1:1 ratio to receive SAIT101 or Rituxan® treatment at Week 24 and Week 26.

Patients who develop an infusion reaction during the second course of treatment should be managed as described in Section 3.2.1.

Patient who are not eligible for the second course of study drug will also attend all visits after Week 24.

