### **3.2.4 Dosage Modification**

Dose modification of rituximab is not permitted during this study. In the event of an infusion-related reaction, the rate of infusion may be adjusted (see Section 3.2.1). Patients who experience a life-threatening event, as considered by the Investigator, during an infusion of study drug should have their infusion stopped and no further infusions should be administered.

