### **3.7.3 Individual Patient**

If a patient discontinues the study treatment prematurely, the reason given must be fully evaluated and recorded appropriately in the source documents and the patient's eCRF. If the patient is discontinued from study treatment because of an AE, that AE should be indicated as the reason for discontinuation.

The Investigator can discontinue treatment of a patient at any time if medically necessary. In addition, patients meeting the patient discontinuation criteria must be discontinued from the study treatment.

Patients will be discontinued from the study treatment in the following circumstances:

- A patient who does not meet the enrolment criteria is inadvertently randomized, that patient must be discontinued from study treatment and the Sponsor or Clinical Research Organization (CRO) must be contacted.
- The Investigator decides that the patient should be discontinued from study treatment. If this decision is made because of an intolerable AE or a clinically significant laboratory value, the study drug is to be discontinued and appropriate measures are to be taken. The Sponsor or designee is to be notified immediately.
- Patient non-compliance, defined as refusal or inability to adhere to the study schedule or procedures (see Section 3.12).
- Treatment with a prohibited concomitant medication other than the use of appropriate medications for the treatment of AEs under the direction of the Sponsor and/or Investigator or Sub-investigator
- Lack of efficacy. Subjects who lack efficacy can be included in the PK and efficacy analysis. Patients receiving rescue therapy prior to Week 24 would not be eligible for second course of infusion.
- Patients who meet any of the following specific safety discontinuation criteria, however can be included for the PK analysis:
  - Patients who develop severe infusion-related reactions, especially severe dyspnea, bronchospasm or hypoxia, should have the infusion interrupted immediately to receive aggressive symptomatic treatment. In all patients, the infusion should not be restarted on the same day until complete resolution of all symptoms. At this time, the infusion may be initially resumed at the discretion of the Investigator at not more than one-half the previous rate. If the same ADRs occur for a second time, the infusion should be permanently discontinued.
  - Active TB

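### For a repeat of the same severe infusion reaction, Protocol 3.2.1 leaves stopping optional while 3.7.3 directs a permanent stop, and the Part B section refers to 3.2.1 without mentioning 3.7.3

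*Protocol*

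**What the plan says.** Three parts of the protocol bear on a severe infusion reaction that comes back.

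- **Section 3.2.1 (dosing, text after Table 1).** After a moderate to severe reaction the infusion is interrupted. It may restart at half the rate once symptoms have gone. One sentence then covers two situations: a patient who cannot tolerate the reduced rate for 30 minutes, and a patient whose reaction recurs. For the second it says "if the same severe (NCI-CTCAE Grade 3) infusion reaction occurs for a second time, the patient can be discontinued from the study treatment".
- **Section 3.7.3 (discontinuation of individual patients).** The general rule is that "patients meeting the patient discontinuation criteria must be discontinued from the study treatment". The list opens "Patients will be discontinued from the study treatment in the following circumstances". Severe infusion-related reactions appear there among the specific safety criteria. The bullet allows a cautious restart at the investigator's discretion after a first reaction, then states "If the same ADRs occur for a second time, the infusion should be permanently discontinued".
- **Section 3.2.3 (Part B).** "Patients who develop an infusion reaction during the second course of treatment should be managed as described in Section 3.2.1". It does not mention 3.7.3.

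Two more serious situations have their own rules. On a life-threatening event during an infusion, Section 3.2.4 says patients "should have their infusion stopped and no further infusions should be administered". Section 3.1 says "Any patient who is suspected of developing PML, anaphylactic reactions, hepatitis reactivation, and severe mucocutaneous reactions will be discontinued from the study treatment", and 3.2.1 separately tells sites to discontinue study drug when anaphylaxis is suspected.

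**The concern.** The same event gets two instructions of different strength. An investigator working from the dosing section, or sent there by the Part B section, finds that stopping is permitted. An investigator working from the discontinuation section finds that a permanent stop is directed.

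What is at stake is mainly patient safety. Infusion reactions are an adverse event of special interest (Section 5.4), and Section 5.4.5 warns that they can be fatal. A patient could be dosed again after a second Grade 3 reaction although another section says treatment should end. About 70 centers could also handle the same event differently. A secondary effect is that the site's choice in Part A can influence which patients are counted in the PK and per-protocol (PP) sets.

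**Working it through.** The question is one of wording, so the check sets the sections side by side. The plan states no figure to reproduce.

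**1. Is it the same event?** Section 3.2.1 speaks of the same severe reaction, at NCI-CTCAE Grade 3, occurring a second time. Section 3.7.3 speaks of severe infusion-related reactions, with severe dyspnea, bronchospasm and hypoxia as leading examples and no grade, and of the same ADRs occurring a second time. The scopes are not identical, but both cover a repeat of the same severe reaction.

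**2. How strong is each instruction?**

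| Place | Verb | Object |
|---|---|---|
| 3.2.1, repeat reaction | can | study treatment |
| 3.7.3, repeat-reaction sentence | should, permanently | the infusion |
| 3.7.3, list opening | will be | study treatment |
| 3.7.3, general rule | must | study treatment |

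Section 3.7.3 itself separates discretion from obligation. It first says the investigator *can* stop treatment whenever medically necessary, then adds that patients who meet the criteria *must* be stopped. On that usage 3.2.1 leaves the repeat reaction to discretion. Section 3.7.3 directs a permanent stop.

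**3. Does another section settle it?** Section 5.4.5 says rituximab may be stopped temporarily or permanently according to severity, and gives no rule for a repeat. Section 3.2.3 refers to 3.2.1. No section states an order of precedence.

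**4. What remains after the other stop rules?** Suspected anaphylaxis (3.1 and 3.2.1) and life-threatening events (3.2.4) are stopped at first occurrence. The gap is therefore a repeat severe reaction that is neither.

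**5. Can the choice reach the analysis sets?** The PK set requires both planned doses (Protocol 6.2.1.1; SAP 4.6, which specifies Part A). SAP Section 13 says a patient whose dose was not fully given is not in that set, whereas an interruption followed by the full dose excludes no parameter. The PP set requires completion of the first course (Protocol 6.2.1.4) or both Part A infusions (SAP 4.5). So if the second reaction occurs in Part A before both doses are complete, stopping takes the patient out of both sets. Resuming and completing the doses leaves the patient potentially eligible. The full analysis set contains all randomized patients and is not affected.

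**6. How often could the rule be needed?** The documents give no rate of repeat severe reactions, so no number of patients can be derived. Only the number of infusions under the rule can be counted:

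- Part A: 282 patients × 2 = 564 planned infusions.
- Both parts, if every patient were retreated: 282 × 4 = 1,128. This is an upper bound, since only patients with an inadequate response at Week 24 are eligible for Part B.

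These are counts of exposure and do not estimate how many patients would be affected.

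**The case against.** The strongest reply is that the two sections are compatible. *Can* permits a stop and does not direct further dosing, and investigators undertake in Appendix 2 to adhere strictly to the whole protocol, 3.7.3 included. That is true of a site that stops. It does not help the site that resumes, because 3.2.1 tells that site its choice is allowed.

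The second reply is that 3.7.3 is softer than it looks. Its repeat-reaction sentence says *should* and concerns the infusion, and the same bullet allows discretionary resumption after a first reaction. Read literally, the list opening would force a stop at the first severe reaction, which the bullet contradicts. This point stands in part. A reader might infer that 3.7.3 states an outright *must* for the repeat reaction, and its own sentence does not. Even so, a directed permanent stop placed among safety discontinuation criteria is clearly stronger than *can*.

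Two further inferences are tempting and not supported:

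- A reader might infer that 3.2.2 orders Day 15 dosing of patients already discontinued, because it says "Patients who experienced infusion-related reactions to the first infusion should receive study drug as per the initial infusion schedule". In context that sentence sets the schedule and rate for patients who go on to a second infusion.
- A reader might infer that 3.2.3 switches off 3.7.3 in Part B. It refers sites to 3.2.1 for management and is silent on 3.7.3.

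Finally, some severe presentations would meet the anaphylaxis criteria in Table 7 and be stopped anyway. That narrows the gap but does not close it.

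**Conclusion.** The concern holds in a limited form. For a second occurrence of the same severe (Grade 3) infusion reaction that is neither anaphylactic nor life-threatening, 3.2.1 makes stopping optional and 3.7.3 directs a permanent stop. The Part B section refers to the weaker text without mentioning the stronger one. This is a wording inconsistency in a patient-safety instruction and should be corrected.

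Its size in patients is unknown and probably cannot be established from the plan. The conclusion rests on reading the two sections as covering the same event, which they do where the reaction is severe under both descriptions.

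A reader might infer that the analyses are untouched because no set definition changes. That goes too far, since an individual's PK and PP membership depends on receiving both Part A infusions. Equally, nothing in the documents shows that enough patients would be involved to alter the equivalence conclusions.

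**What to change.** **Section 3.2.1.** Split the sentence. Keep stopping at the investigator's discretion for a patient who does not tolerate the reduced rate. State separately that when the same NCI-CTCAE Grade 3 infusion reaction recurs, the infusion must be stopped and study treatment permanently discontinued, with a reference to Section 3.7.3.

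**Section 3.2.3.** Refer Part B infusion reactions to Sections 3.2.1 and 3.7.3.

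**Cost.** A wording amendment, ethics committee approval before it takes effect (Section 13), and notice to about 70 centers. No new procedure, eCRF field or SAP change is needed. A few patients who might have resumed dosing in Part A may leave the PK and PP sets. They would not be lost to follow-up by design, because 3.7.3 keeps patients who stop study drug in all visits to Week 52.

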### **3.2.2 Study Drug Administration (Part A)**

#### **First Infusion (Day 1 of First Course)**

The first infusion rate of SAIT101 or MabThera® or Rituxan® will be 50 mg/hour; after the first 30 minutes, it can be escalated in 50 mg/hour increments every 30 minutes, to a maximum of 400 mg/hour (see Table 1).

#### **Second Infusion (Day 15 of First Course)**

Patients who experienced infusion-related reactions to the first infusion should receive study drug as per the initial infusion schedule, with the rate of infusion not exceeding half that associated with the prior reactions. If this reduced rate is tolerated for 30 minutes, then the infusion rate may be increased to the next closest rate following the infusion schedule.

Patients who miss the allocated day (Day 15  $\pm$  1 day) for the second infusion (the first infusion will be administered following randomization on Day 1) will be contacted and another visit arranged as soon as practically possible in order to administer study drug. Such cases will be considered protocol deviations (see Section 3.13).

If a patient experiences a new infection or other AE between the Day 1 and Day 15 infusions of any treatment, the Day 15 infusion should be delayed until the infection or AE has completely resolved and the Investigator considers it safe to resume treatment. A maximum delay of 15 days from the scheduled date of the second infusion is permitted. Patients who have a delay of >15 days in receiving the second infusion due to an AE or otherwise will be discontinued from the study treatment.

### **3.2.3 Study Drug Administration (Part B)**

Patients with active rheumatoid arthritis (<50% improvement from Baseline in both the swollen and tender joint counts) who have been followed up during Part A will be provided with continued (or additional) treatment of rituximab.

Before subsequent dose, absolute neutrophil count must be  $\geq 1.5 \times 10^9/L$  and platelet counts must be  $\geq 75 \times 10^9/L$ . If the Absolute Neutrophil Count (ANC) value and platelet count are marginally lower, re-testing at an unscheduled visit may be performed at the discretion of the Investigator within the 4-week period between Week 20 and Week 24. In case Visit 11 is missed, all safety evaluations including ANC value and platelet count must be completed as an unscheduled visit for patient to be eligible for second course of infusion.

Eligible patients in the SAIT101 arm will receive additional SAIT101 treatment at Week 24 and Week 26. Eligible patients in the MabThera® arm will receive additional MabThera® treatment at Week 24 and Week 26. Eligible patients in the Rituxan® arm will be randomized in a 1:1 ratio to receive SAIT101 or Rituxan® treatment at Week 24 and Week 26.

Patients who develop an infusion reaction during the second course of treatment should be managed as described in Section 3.2.1.

Patient who are not eligible for the second course of study drug will also attend all visits after Week 24.

### **3.2.4 Dosage Modification**

Dose modification of rituximab is not permitted during this study. In the event of an infusion-related reaction, the rate of infusion may be adjusted (see Section 3.2.1). Patients who experience a life-threatening event, as considered by the Investigator, during an infusion of study drug should have their infusion stopped and no further infusions should be administered.

